kg	Kilogram
LLDAS	Lupus Low Disease Activity State
LLOQ	Lower limit of quantitation
LOCF	Last observation carried forward
m	Meter
MACE	Major adverse cardiovascular event
MAR	Missing at random
MedDRA	Medical Dictionary for Regulatory Activities
mITT	Modified intention-to-treat
mmHg	Millimeters of mercury
nAb	Neutralizing antibodies
NR	Non-response or non-responder
NSAIDs	Nonsteroidal anti-inflammatory drugs
OCS	Oral corticosteroids
PD	Pharmacodynamic

Abbreviation or Specialized Term	Definition
PD Plan	Protocol deviation plan
PEOT	Premature end of treatment
PGA	Physician's Global Assessment
PK	Pharmacokinetic(s)
PT	Preferred Term
Q4W	Every 4 weeks
QoL	Quality of life
RM	Restricted medication use
SAE	Serious adverse event
SAP	Statistical analysis plan
SBP	Systolic blood pressure
SD	Standard deviation
SDI	Systemic Lupus International Collaborating Clinics/American College of Rheumatology Damage Index
SI	International System of units
SLE	Systemic lupus erythematosus
SLEDAI-2K	Systemic Lupus Erythematosus Disease Activity Index 2000
SOC	System organ class
SRI(X)	Systemic Lupus Erythematosus Responder Index of $\geq X$
TELVC	Treatment emergent laboratory/vital signs changes
ULN	Upper limit of the normal
VAS	Visual analogue scale
WDS	Withdraw from study
WHO-DD	WHO Drug Dictionary
WPAI	Work productivity and activity impairment

AMENDMENT HISTORY

CATEGORY Change refers to:	Date	Description of change	In line with CSP?	Rationale
N/A	06-Nov-2021	Initial draft SAP	Yes, version 1.0	N/A
Derivation of secondary endpoint(s)	05-Jan-2024	Added text “compared to baseline” in section 4.2.13.1.	Yes, version 3.0	To clarify the definition of participants who achieve Major Clinical Response.
Data presentation	05-Jan-2024	Updated that Week 56 is 8 weeks after last dose and Week 60 is 12 weeks after last dose in section 3.3.1.2.	Yes, version 3.0	To clarify the study periods.
Primary endpoint(s)	05-Jan-2024	Clarified the LOCF logic for the primary endpoints, relevant secondary and exploratory endpoints, and that LOCF records are not used in the repeated measures models.	Yes, version 3.0	To clarify the LOCF logic and the method of imputing missing data using LOCF in this study.
Primary endpoint(s)	05-Jan-2024	Added information for SLEDAI-2K in section 4.1.6.1.	Yes, version 3.0	To clarify the definition of SLEDAI-2K scores.
Data presentation	05-Jan-2024	Remove reference Appendix U from the CSP.	Yes, version 3.0	Removed as this Appendix is not in the CSP.
Data presentation	05-Jan-2024	Updated period for C-SSRS to use “treatment and follow-up period” in section 4.6.6.1.	Yes, version 3.0	To clarify the reporting period for C-SSRS.

CATEGORY Change refers to:	Date	Description of change	In line with CSP?	Rationale
Data presentation	05-Jan-2024	Add reference range for U-Protein test in 7.2. Add INR and total Cholesterol ranges to 7.2.	Yes, version 3.0	Information added for the analysis.
Data presentation	05-Jan-2024	Added text to define the number of total expected dose in the calculation of Drug compliance % in section 4.1.9.1.	Yes, version 3.0	To clarify the definition of total expected dose.
Data presentation	05-Jan-2024	Updated Table 4 to Table 3 in text in section 4.2.16.	Yes, version 3.0	To correct the typo.
Secondary endpoint(s)	05-Jan-2024	Removed supplementary analysis targeting the impact of PEOT and/or RM for CLASI. Moved flares endpoint to objective 4 as key secondary endpoint. Moved CLASI to objective 5 as other secondary endpoint.	Yes, version 3.0	To follow the updated CSP v3.0.
Secondary endpoint(s)	05-Jan-2024	Added text “Individual components of BICLA and SRI(4) at weeks 24 and 52 will be presented in a table by treatment group.” To section 4.2.10.4.	Yes, version 3.0	To justify the analysis for individual component of BICLA and SRI(4).
Primary endpoint(s)	05-Jan-2024	Updated formula in part D and F of section 4.2.1.5	Yes, version 3.0	To clarify the formula for the primary analysis.

CATEGORY Change refers to:	Date	Description of change	In line with CSP?	Rationale
Data presentation	05-Jan-2024	Updated the rounding rules for decimal places in section 3.3.	Yes, version 3.0	To follow AZSOL guiding principle.
Data presentation	05-Jan-2024	Added criteria for treatment emergent changes for urinalysis for Glucose, Ketone Bodies, and qualitative Erythrocytes in section 4.6.3.2.	Yes, version 3.0	To provide information for the analysis.
Secondary endpoint(s)	05-Jan-2024	Added PEOT and Death in the calculation of exposure time and number of flares in section 4.2.4.2.	Yes, version 3.0	To clarify the calculation of flare endpoint.
Data presentation	05-Jan-2024	Added text to define “screening” analysis window in section 3.3.1.2.	Yes, version 3.0	To clarify the analysis window.
Secondary endpoint(s)	05-Jan-2024	Updated to “Not applicable” in section 4.2.16.3.	Yes, version 3.0	To update the missing data imputation rule for Lupus QoL.
Secondary endpoint(s)	15-Jan-2024	Updated LLDAS definition in section 4.2.14.1.	Yes, version 3.0	To follow the definition in protocol v3.0.
Data presentation	15-Jan-2024	Updated “AEs occurring during treatment period including follow-up period” to “AEs occurring during treatment period and follow-up period” in section 4.6.2.1.	Yes, version 3.0	To align with previous anifrolumab studies at program level

CATEGORY Change refers to:	Date	Description of change	In line with CSP?	Rationale
Data presentation	15-Jan-2024	Updated region group “Others” to “not mainland China” in section 3.2, 4.1.1.2, 4.2, 4.2.1.5 4.2.1.8, 4.2.2.6, 4.2.3.4, 4.2.3.6, 4.2.4.8, 4.2.9.4.	Yes, version 3.0	To follow protocol v3.0.
Primary endpoint(s)	15-Jan-2024	For primary/key secondary/other secondary endpoint, no PEOT, no RM are removed from the response criteria. Instead, these are handled through ICE strategies. Changes were made to section 4.2.1.1, 4.2.1.3, 4.2.2.1, 4.2.2.3, 4.2.3.1, 4.2.3.3, 4.2.5.1, 4.2.5.3, 4.2.6.1, 4.2.6.3, 4.2.14.1, 4.2.14.3.	Yes, version 3.0	To follow protocol v3.0.
Data presentation	13-Feb-2024	Changed the number of randomized patients from 328 to 260 in section 3.2.	Yes, version 3.0	To follow protocol v3.0.
Data presentation	13-Feb-2024	Added abbreviation for ANA, ICU, MAR to the List of Abbreviations.	Yes, version 3.0	To add the required information.
Data presentation	08-Apr-2024	Update the missing day and missing day and month imputation rule in section 3.3.1.3	Yes, version 3.0	To correct the imputation rule.

CATEGORY Change refers to:	Date	Description of change	In line with CSP?	Rationale
Primary endpoint(s)	10-Apr-2024	For the primary endpoint, the stratified Cochran-Mantel-Haenszel (CMH) analysis is now a supportive analysis. The primary analysis will use the Bayesian robustified mixture prior approach with borrowing from the pooled global phase III studies (study 05 and study 04). This change applies to section 4.2.1.4 and 4.2.1.5.	Yes, version 3.0	To follow protocol v3.0.
Primary endpoint(s)	16-Jul-2024	For the time to BICLA analysis in section 4.2.1.7.7, updated the title to include “Supplementary Analysis of the Primary Endpoint”. Clarified that intercurrent events are considered as non-responders per the primary BICLA endpoint, with time at risk based on the latest assessment during the double blind treatment period.	Yes, version 3.0	To clarify the handling of intercurrent events for the analysis.
Secondary endpoint(s)	16-Jul-2024	Removed flares versus baseline analysis in section 4.2.4.7.	Yes, version 3.0	Removed the analysis as robust results were observed between flare versus the previous visit and flare versus baseline.

CATEGORY Change refers to:	Date	Description of change	In line with CSP?	Rationale
Secondary endpoint(s)	16-Jul-2024	Replace “BICLA” with “BILAG” in the title of section 4.2.1.7.6.	Yes, version 3.0	To correct the text.
Primary endpoint(s)	26-Jul-2024	Edited Table 2 to reflect the analyses performed.	Yes, version 3.0	To provide the correct list of analyses.
Primary endpoint(s)	26-Jul-2024	Added text to reference BICLA response definition in section 4.2.1.7.7.	Yes, version 3.0	To provide more information.
Primary endpoint(s)	29-Jul-2024	Added new section 4.2.1.7.1 to add the supplementary analysis targeting the impact of PEOT due to different reasons. Table 2 was updated.	Yes, version 3.0	To evaluate the impact of PEOT due to different reasons.
Secondary endpoint(s)	29-Jul-2024	Updated the rule for dropouts and missing data handling in section 4.2.4.3.	Yes, version 3.0	To clarify how to handle dropouts and missing data for flare related analyses.
Data presentation	30-Jul-2024	Removed changes under “Changes to protocol Planned analyses” section as all the planned analyses are now following the latest CSP v3.0.	Yes, version 3.0	To update according to the latest CSP v3.0.
Data presentation	04-Sept-2024	Update text “Week 0 (Day 1) OCS dose” to “Randomization (day 1) OCS dose” throughout the SAP.	Yes, version 3.0	To update according to the latest CSP v3.0.

CATEGORY Change refers to:	Date	Description of change	In line with CSP?	Rationale
Secondary endpoint(s)	04-Sept-2024	Removed section 4.2.4.5.2 Missing data imputation analysis for flares.	Yes, version 3.0	Robust results observed based on global studies. Remove to avoid repeated analysis.
Secondary endpoint(s)	04-Sept-2024	Removed section 4.2.5.5.1 sensitivity analysis targeting the impact of PEOT and/or RM, tipping point analysis and section 4.2.5.6 subgroup analyses for skin lesions.	Yes, version 3.0	Reduce the number of sensitivity analysis as CLASI has been downgraded to other secondary endpoint per CSP 3.0.
Secondary endpoint(s)	16-Sept-2024	Updated the table “Conversion factors to oral prednisone equivalent dose” in Appendix 7.4.	Yes, version 3.0	To include all the OCS potentially used in the study.
Secondary endpoint(s)	17-Sept-2024	Updated that Pharmacokinetics is analyzed by IFN gene status not by treatment group in section 4.2.7.4.	Yes, version 3.0	PK parameters are only tested for active group.
Data presentation	18-Oct-2024	Removed Appendix D – ECG Potentially clinically significant post-baseline values.	Yes, version 3.0	To reflect no numerical ECG data is collected in this study.
Data presentation	18-Oct-2024	Updated the Herpes zoster classification in section 4.6.2.1.	Yes, version 3.0	To reflect the data collection approach.

CATEGORY Change refers to:	Date	Description of change	In line with CSP?	Rationale
Data presentation	23-Oct-2024	Added new section 3.3.7 - Identifying Cases of PEOT Due to Lack of Therapeutic Response and section 3.3.8 - Identifying Cases of PEOT due to COVID Lockdown.	Yes, version 3.0	To reflect the data collection approach.
Data presentation	23-Oct-2024	Removed Appendix A - Derivation of Prednisone Equivalent Daily Dose. Moved the content from this Appendix A to the current Appendix D - Restricted and prohibited medications – Programmatic Rules. Update the rules in Appendix D.	Yes, version 3.0	To clarify the programmatic rules for restricted and prohibited medications, keep alignment with anifrolumab program level.
Data presentation	24-Mar-2025	Capitalize Lupus-QoL Domains in Table 3 in section 4.2.16.1.	Yes, version 3.0	To follow industry standards.
Data presentation	24-Mar-2025	Pharmacokinetics by ADA status figure description updated in section 4.2.7.4.	Yes, version 3.0.	To align with previous anifrolumab studies.
Secondary endpoint(s)	25-Mar-2025	Section 3.3.9 added to describe EQ-5D-5L data excluded from analysis based on Clinical Data Standards and Dictionary Waiver Form (AZDoc0165290).	Yes, version 3.0.	To clarify that only data without errors is included for analysis.

CATEGORY Change refers to:	Date	Description of change	In line with CSP?	Rationale
Data presentation	25-Mar-2025	Section 3.3.1.2 change phrasing “primary and secondary endpoints” to “efficacy endpoints and pharmacodynamics endpoints including complements and anti-dsDNA” are assessed during the double-blind treatment period.	Yes, version 3.0.	To clarify the data included for efficacy analyses.
Secondary endpoint(s)	25-Mar-2025	Sections 4.2.4.2, 4.2.4.3 and 4.2.4.6 updated to clarify that LOCF records are included in analyses, and clarify the analysis periods for the primary and on-treatment analyses.	Yes, version 3.0.	To clarify the data included for efficacy analyses.
Derivation of secondary endpoint(s)	25-Mar-2025	Section 4.6.2.1 update the definition for opportunistic and non-opportunistic infections to align to AESIs.	Yes, version 3.0.	To clarify the derivation rules.
Data presentation	25-Mar-2025	Sections 4.6.2.1 and 4.6.2.2 Added definitions, derivations and analyses for AE exposure adjusted incidence rates.	Yes, version 3.0.	To clarify the derivation rules and types of AEs to be summarized by EAIR.

CATEGORY Change refers to:	Date	Description of change	In line with CSP?	Rationale
Data presentation	25-Mar-2025	Section 4.7 update to use China subpopulation (instead of China cohort and China Analysis sets).	Yes, version 3.0.	Per CSR requirement.
Data presentation	25-Mar-2025	Appendix B Added Urine Glucose, Ketone Bodies and qualitative Erythrocytes to tests.	Yes, version 3.0.	To clarify all the tests to be presented.
Data presentation	07-Apr-2025	Section 4.6 clarify that safety presents for the treatment and follow-up period, unless otherwise specified. Section 4.6.7.2 clarify that analysis reports the treatment period.	Yes, version 3.0	To clarify the data presentation.
Data presentation	07-Apr-2025	Section 4.1.8 updated to present restricted medication ICE, instead of On IP/Off IP restricted medications.	Yes, version 3.0	To clarify the data presentation. To align to restricted medication process.
Data presentation	09-Apr-2025	Section 3.3 added R version used for primary analysis of the primary endpoints.	Yes, version 3.0	To clarify software version ensuring reproducibility of results.
Secondary endpoint(s)	29-Apr-2025	Section 4.2.4 clarify that stratification factor can be exclude from the covariates of model when there are limited events in the corresponding stratum	Yes, version 3.0	To maintain model stability and robustness in case of limited events.

CATEGORY Change refers to:	Date	Description of change	In line with CSP?	Rationale
Data presentation	29-Apr-2025	Section 4.2.8.1 clarify the definitions and derivation for ADA categories	Yes, version 3.0	To clarify the definitions and derivation for ADA categories
Primary endpoint(s)	29-Apr-2025	Section 4.2.1.6 and Table 2 Added a supportive analysis of the Primary Estimand: Bayesian Borrowing based on odds ratio.	Yes, version 3.0	To evaluate the robustness of Bayesian dynamic borrowing approach
Primary endpoint(s)	12-May-2025	Section 4.2.1.4 clarify the prior weights and thresholds used in primary analysis.	Yes, version 4.0	To align with the latest CSP

1 INTRODUCTION

The purpose of this document is to give details for the statistical analysis of study D3468C00003, a multicenter, multinational, randomized, double-blind, placebo-controlled study to evaluate the efficacy and safety of an intravenous (IV) treatment regimen of 300 mg anifrolumab versus placebo in adult Asian participants with moderate to severe active, autoantibody-positive systemic lupus erythematosus (SLE) despite receiving standard of care treatment.

This statistical analysis plan (SAP) provides details of the summaries and analyses to be performed to support the clinical study report (CSR) of the study. The reader is referred to the latest version of the clinical study protocol (CSP) of the study D3468C00003.

2 CHANGES TO PROTOCOL PLANNED ANALYSES

No change to protocol planned analyses listed in CSP v3.0.

3 DATA ANALYSIS CONSIDERATIONS

3.1 Timing of Analyses

There will be 2 clinical database locks (CDLs) in the study. The primary analysis CDL will occur after all randomized participants have completed Week 52 (or have withdrawn from the study). The primary analysis CDL includes the assessments of the primary, key secondary, and secondary objectives, including safety. Exploratory objectives available at the time of the primary CDL may also be included. No changes to the clinical database up to Week 52 will be made once the primary CDL has occurred. The final analysis CDL will be performed after all participants have completed their last visits/assessments.

3.2 Analysis Populations

Approximately 260 eligible participants receiving standard of care treatment are randomized in a 1:1 ratio to receive either a fixed IV dose of 300 mg anifrolumab or placebo every 4 weeks (Q4W) for a total of 13 doses (Week 0 to Week 48), with the primary endpoint evaluated at the Week 52 visit.

Randomization will be stratified using the following factors: Systemic Lupus Erythematosus Disease Activity Index 2000 (SLEDAI-2K) score at screening (<10 points versus ≥ 10 points); randomization (Day 1) oral corticosteroids (OCS) dose (<10 mg/day versus ≥ 10 mg/day prednisone or equivalent); and region (mainland China versus not mainland China).

3.2.1 All Participants Analysis Set

All participants who signed the informed consent form (ICF). The all participants analysis set is used to summarize disposition and screening failures.

3.2.2 Full Analysis Set

The full analysis set (FAS) is used as the primary population for reporting efficacy. This comprises all participants randomized into the study who receive at least 1 dose of investigational product (IP) and is analyzed according to randomized treatment (modified Intention-To-Treat [mITT]).

3.2.3 Safety Analysis Set

The safety analysis set consists of all participants who have received at least 1 dose of IP. Erroneously treated participants, who are randomized to receive anifrolumab but are actually given placebo for the entirety of their time in the study, are accounted for in the placebo arm. A participant who has on one or several occasions received anifrolumab is classified in the respective anifrolumab group. This population is used in the analysis of safety endpoints.

3.2.4 Pharmacokinetic Analysis Set

The pharmacokinetic (PK) analysis set consists of all participants in the FAS who received anifrolumab and who have at least 1 quantifiable serum PK observation post first dose, with no protocol deviations thought to significantly impact on the analysis of the PK data.

The exclusion of any participants or time points from the calculation of the PK parameters are documented, including the reasons for exclusion. The available concentration data and PK parameter data for any participants excluded from the PK analysis set is listed only.

The PK analysis set is used to summarize the PK data.

3.3 General Considerations

- Summary tables are produced by treatment group (Anifrolumab 300mg and Placebo) unless otherwise stated. Total columns are produced only for tables of study population data, unless otherwise stated.
- Continuous variables are summarized by the number of non-missing observations, mean, standard deviation (SD), median, and the minimum and maximum as appropriate.
- Log-transformed continuous variables are summarized in a similar manner. The geometric mean and coefficient of variation (CV%), median, minimum and maximum are

presented as appropriate. In addition, the relative change from baseline is calculated by back-transforming the change from baseline of the logarithmic variable as necessary.

- Categorical variables are summarized as counts (n) and percentages (%). Unless otherwise stated, percentages are calculated using the relevant analysis set population total by treatment group as the denominator. Percentages are rounded to one decimal place; except 100% which are displayed without any decimal places. Percentages are not to be presented for zero counts.
- If a model is used to estimate the treatment difference, the corresponding confidence interval (CI) according to the model is presented. Otherwise, the unadjusted CI is used.
- Mean, SD, medians, 1st quartile and 3rd quartile are rounded to one additional decimal place relative to the original data, the maximum, minimum will be displayed with the same accuracy as the original data and the CV% is presented with 1 decimal place. The statistics are displayed in the order of n, mean, minimum, first quartile (optional), median, third quartile (optional), maximum. 95% CIs are presented for treatment comparison to one more decimal place than the raw data. For the confirmatory treatment comparisons, p-values will be reported to 3 decimal places. Percentages (proportion) will be rounded to one decimal place.
- Summaries are provided by time point of assessment where appropriate. Where summaries are by time point, study day is calculated in relation to the date of first dose of study treatment. For assignment of data to time points using the visit windows, study day is calculated in relation to the date of first dose of investigational product.
- Study Day 1 is defined as the day of first study drug administration.
- Study Days prior to the date of first study drug administration, are defined as:
(Date of assessment – date of first administration of IP)
- Study Days after the first dose of investigational product, are defined as:
(Date of assessment – date of first administration of IP) + 1. Using this definition, the day of first dose of IP is Day 1 and the scheduled visit date of Week 4 is study day 29 (=28+1) for example.
- Corresponding listings are provided for certain results unless stated otherwise. Any additional listings that are required will be described in the appropriate sections of the SAP. The listings are sorted by treatment group and subject number.

- SAS® version 9.4 or higher will be used for all data analyses, except for Bayesian Dynamic Borrowing approach (Section 4.2.1.4 and 4.2.1.6), which was implemented using the RBesT package in R (version 3.6.3 or higher).

3.3.1 General Study Level Definitions

3.3.1.1 Definition of Baseline

Baseline is defined as the last measurement prior to the first dose administration of anifrolumab on Day 1. If the Day 1 value is missing or is invalid or is collected after administration of IP, the latest assessment prior to dose administration on Day 1 serves as baseline.

3.3.1.2 Study Periods

The allocation to the study periods is performed after any imputation of missing dates (for AEs only) as described in Section 3.3.1.3. The study periods are defined as follows:

- Screening Period: Up to 35 days.
- Double Blind Treatment Period: A 52-week double-blind treatment period from first dose of IP through Week 52 visit or date of study withdrawal/lost to follow-up (FU)/death/ Early discontinuation visit (EDV), whichever comes first; efficacy endpoints and pharmacodynamics endpoints including complements and anti-dsDNA are assessed during the double-blind treatment period.
- Safety Follow-up: After Week 52 or the date of EDV (the completion of the double-blind treatment period), participants may continue in the study for further 8 weeks to complete the safety follow-up period, which is comprised of two visits, at Week 56 (or 8 weeks after the last dose) and Week 60 (or 12 weeks after the last dose).

Measurements on Study Day 1 are with a time prior to the first IV administration of IP, use the study period label as “Screening”. If any of the measurement occurs after the start time of IP administration, the study period label is as “Treatment”. In case of the time of measurement at Study Day 1 is not available, it is assumed to be prior to first administration of IP and study period label is “Screening”. If the measurement is after Week 52 or Early Withdrawal and participants will continue in the study for further 8 weeks to complete the safety follow-up period, then the study period label is as “Safety Follow-up”.

Study periods for the analyses of adverse events (AE) are defined separately in Section 4.6.2.1.

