#### **4.3.1 Follow up visits after premature discontinuation of investigational medicinal product**

**Participants who discontinue investigational medicinal product (see Section 3.9) will be asked to return for all regularly scheduled clinic visits.** If the participant is unwilling to complete all regularly scheduled clinic visits, the participant should complete the EDV within 4 weeks of the last dose of investigational medicinal product, as well as Follow-up Visit 1 and Follow-up Visit 2 (8 and 12 weeks after the last dose) unless consent is withdrawn.

If the participant is unwilling to continue with any study visits, including EDV visit, at a minimum, the following assessments should be completed:

- SLEDAI-2K and the associated laboratory tests (anti-dsDNA antibodies, C3, C4, CH50).
- BILAG-2004 laboratory tests to include anticardiolipin, lupus anticoagulant, haptoglobin and Coombs (Coombs will be performed at local laboratory as applicable per BILAG assessment requirements).
- Note: In order to avoid having to bring the participant back for a separate phlebotomy, the anticardiolipin, lupus anticoagulant, and haptoglobin blood specimen will be collected at all specified visits, however the blood will be stored at the central laboratory, and the analyses performed only if Investigator indicates that these tests need to be completed because of clinical suspicion of haemolytic anaemia or antiphospholipid syndrome. Direct Coombs test samples will only be collected per Investigator's opinion at local laboratory and applicable BILAG assessment requirements for determining haemolytic anaemia.
- CLASI
- PGA
- Joint count

The following safety assessments will also be completed:

- Serum chemistry, haematology, urinalysis
- Urine for protein, creatinine and urine-protein-creatinine ratio
- Lipid Profile defined in Section 5.2.1.1
- Immunology Profile defined in Section 5.2.1.1
- Vital signs
- Complete physical examination, weight
- AE including AESIs
- Cardiovascular risk assessment

- TB questionnaire
- Concomitant medications

If the participant does not agree to do this, they will be asked if they can be followed on a monthly basis via telephone calls until 12 weeks post the last dose of IMP. At these calls, they will be asked about AEs/SAEs, lupus symptoms, and lupus medications. Steroid bursts will also be captured.

Adverse events will be followed up per Section 6.4.2.

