#### **8.5 Methods for statistical analyses**

The analysis of the primary and secondary endpoints will include all data captured during the 52-week treatment period, regardless of whether study treatment was prematurely discontinued, or delayed, and/or irrespective of protocol adherence.

In general, the analyses will be based on the FAS unless otherwise stated. Intercurrent events are defined as events occurring after treatment initiation that affect either the interpretation or the existence of the measurements associated with the clinical question of interest. In this study the intercurrent events are:

- Restricted medication use,
- Premature end of treatment,
- Death

The strategy for dealing with the intercurrents events will be detailed for the primary analyses of the primary endpoint. The strategy for all other endpoints will be detailed in the SAP.

Supplementary estimand/sensitivity analyses for the primary and key secondary endpoints for assessing the robustness of results will explore different methods for handling intercurrent events and different assumptions for missing data. The impact of non-compliance due to COVID-19 on PEOT will also be evaluated using hypothetical strategy with multiple imputation as supplementary analysis. Full details will be provided in the SAP.

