4.2.4.2 Derivations

The occurrence of a new flare will be checked for each available visit versus the previously available visit up to Week 52. If no flare occurred, the number of flares will be set to 0. Otherwise, all flares will be counted leading to a maximum number of flares of 13.

The annualized flare rate is calculated as the number of flares divided by the flare exposure time in days multiplied with 365.25. The flare exposure time is the time up to the date of last available BILAG-2004 assessment up to and including Week 52 during the double-blind treatment period. It is derived as the date of last BILAG-2004 assessment minus date of first administration of IP + 1.

For the supplementary analyses of flares while on treatment, the flare exposure time is the time up to the date of last dose of IP + 28 days. It is derived as date of last dose of IP + 28 days - date of first dose of IP + 1. All flares occurring within the double-blind treatment period and the flare exposure time are considered for this analysis.

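### For participants who take the early discontinuation visit, the SAP's period definition ends the treatment-policy flare analyses at about the on-treatment cut, and other SAP wording conflicts with that definition

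*SAP*

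**What the plan says.** **Period definition.** SAP 3.3.1.2 runs the double-blind period from first dose to the Week 52 visit, withdrawal, loss to follow-up, death or "Early discontinuation visit (EDV), whichever comes first". It adds that "efficacy endpoints and pharmacodynamics endpoints including complements and anti-dsDNA are assessed during the double-blind treatment period". A later sentence, beginning "If the measurement is after Week 52 or Early Withdrawal", gives such measurements the safety follow-up label.

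**Flare derivation.** SAP 4.2.4.2 ends flare exposure at the "last available BILAG-2004 assessment up to and including Week 52 during the double-blind treatment period". The counting rule in the same section carries no period restriction: "The occurrence of a new flare will be checked for each available visit versus the previously available visit up to Week 52". SAP 4.2.4.3, on participants who stop treatment early, also refers only to Week 52. The while-on-treatment analysis ends exposure at last dose plus 28 days.

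**Declared strategy.** SAP Table 2 gives the primary flare analysis, its tipping-point analysis, time to first flare and the flare subgroups a treatment-policy strategy for premature end of treatment (PEOT). SAP Section 2 declares no change from the protocol's planned analyses.

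**Protocol.** Section 4.3.1 asks those who stop treatment to keep attending regular visits. Those unwilling have an EDV within 4 weeks of the last dose, then "Follow-up Visit 1 and Follow-up Visit 2 (8 and 12 weeks after the last dose) unless consent is withdrawn". Protocol Table 5 collects BILAG-2004, SLEDAI-2K and PGA at both follow-up visits. For primary and secondary endpoints alike, Section 8.5 says that the analysis "will include all data captured during the 52-week treatment period, regardless of whether study treatment was prematurely discontinued".

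**The concern.** A treatment-policy strategy uses what is observed after treatment stops. Under the period definition, a participant on the EDV route contributes flare data only to the EDV, although two later BILAG-2004 assessments usually exist inside the 52 weeks. For that participant the main flare analysis and the while-on-treatment analysis nearly coincide, so comparing the two cannot show the effect of PEOT that the supplementary analysis targets. The weeks dropped are those just after treatment ends.

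The second problem is reproducibility. One sentence restricts exposure to the double-blind period, while the counting sentence does not. Two programmers following the SAP could produce different flare rates for a key secondary endpoint.

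**Working it through.** **Inputs.** Four-weekly visits (Protocol Table 4); EDV by 4 weeks and follow-up visits at 8 and 12 weeks after the last dose (Protocol 4.3.1); Week 48 window Days 323–350 and Week 52 window Days 351–378 (SAP Table 1); 130 participants per arm (Protocol 8.2).

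**The plan's own figure.** SAP 4.2.4.2 gives a maximum of 13 flares. Post-baseline visits at Weeks 4, 8, …, 52 number 52/4 = 13, so it is reproduced.

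**Where the visits fall.** Study day = 7 × week + 1. For a last dose at week L, the nominal visits are the EDV at L + 4, Follow-up Visit 1 at L + 8 and Follow-up Visit 2 at L + 12. Flare exposure (last assessment date − first dose date + 1) equals the study day of the last assessment used.

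| Last dose | EDV day | FU1 day | FU2 day | Exposure to EDV | Exposure to last FU by Week 52 | Days lost | Share lost |
|---|---|---|---|---|---|---|---|
| Week 0 | 29 | 57 | 85 | 29 | 85 | 56 | 65.9% |
| Week 20 | 169 | 197 | 225 | 169 | 225 | 56 | 24.9% |
| Week 36 | 281 | 309 | 337 | 281 | 337 | 56 | 16.6% |
| Week 40 | 309 | 337 | 365 | 309 | 365 | 56 | 15.3% |
| Week 44 | 337 | 365 | 393 | 337 | 365 | 28 | 7.7% |

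For every last dose from Week 0 to Week 40, both follow-up visits fall by Day 365. For Week 44, only the first does.

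**Overlap with the on-treatment analysis.** On-treatment exposure is (7L + 1) + 28 = 7L + 29 days. Exposure to a nominal EDV is 7(L + 4) + 1 = 7L + 29 days, which is the same.

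**Count and exposure out of step.** Take a last dose at Week 20 and one flare, first seen on Day 197. If the flare is counted but exposure stops at the EDV, the participant's annualised rate is 1/169 × 365.25 = 2.16. With exposure to Day 225 it is 1/225 × 365.25 = 1.62. With both cut at the EDV it is 0.

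**BICLA and SRI(4) analyses that ignore PEOT** (SAP 4.2.1.7.2 and 4.2.1.7.5, and their SRI(4) counterparts in 4.2.2.5):

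- Last dose Week 40: the visits on Days 337 and 365 are excluded, so Weeks 48 and 52 are both missing. LOCF applies once, so Week 52 becomes non-response although a Day 365 assessment exists.
- Last dose Week 44: the Day 365 assessment is excluded and replaced by the EDV value in the Week 48 window.
- Last dose Week 36: the Day 337 assessment, which LOCF could have carried to Week 52, is excluded.

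**Overall size.** The documents do not give the share of participants on the EDV route. Call it s. If all of them had a last dose by Week 40 and attended both visits, the loss is s × 56/365.25 of a maximum one year each:

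- s = 3% (10% stopping × 30% taking the EDV route): 0.46%
- s = 5%: 0.77%
- s = 10%: 1.53%
- s = 14% (20% × 70%): 2.15%
- s = 20%: 3.07%

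Per arm, 5% is 6.5 participants, 13 assessments and 1.0 patient-year; 20% is 26 participants, 52 assessments and 4.0 patient-years.

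**The case against.** The protocol can be read as placing these visits outside the treatment period. Its Section 4.5 and Table 5 treat them as follow-up, Section 3.9.3 speaks of safety follow-up, and Table 4 makes the EDV a closing visit of the double-blind period. On that reading SAP 3.3.1.2 mirrors the protocol. This stands to the extent that an outright contradiction of Protocol 8.5 cannot be claimed; the mismatch is with its evident intent and with the treatment-policy label.

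The SAP also does not exclude the data uniformly. The flare-count sentence, SAP 4.2.4.3 and the study-day windows all run to Week 52 without mentioning the EDV. This stands too. A reader might infer that the assessments will certainly be discarded, but the documents support only that one set of sentences excludes them and another does not.

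SAP 4.2.4.5 varies the post-withdrawal flare rate, with multipliers of 1 to 4.5 for anifrolumab and 0.22 to 1 for placebo. That explores unobserved rates, and its tipping-point part runs only if p ≤ 0.05. It is no reason to leave out observed data.

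Finally, the size rests on assumed shares, and some EDVs are done at study withdrawal (Protocol 3.10.2) with nothing later to recover. This stands, and it makes the figures above more likely too high than too low.

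**Conclusion.** The point holds as a limited defect. For EDV-route participants the SAP's period definition makes the treatment-policy flare analyses end at about the on-treatment cut, and the SAP is inconsistent on whether later assessments up to Week 52 count. The loss is at most two assessments, about 8 weeks, per such participant. Across the trial it is probably small: roughly 0.5% to 3% of exposure for EDV-route shares of 3% to 20%, which are assumptions.

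Two stronger inferences are not supported. The primary result is not affected: PEOT is already non-response in the primary BICLA analysis and in the main SRI(4) analysis, and participants who stop treatment but keep attending regular visits keep their data. Nor has a biased flare comparison been shown. Lost flares and lost exposure leave together if one cut is used, the documents give no discontinuation rates by arm, and no change in the rate ratio has been calculated. The p-value for flares is nominal in any case (SAP 3.3.4).

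**What to change.** Before unblinding, amend SAP 3.3.1.2, 4.2.4.2 and 4.2.4.3 for the treatment-policy analyses:

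- Define the efficacy period as first dose to the Week 52 visit (or Day 378, the end of its window, if there is none), study withdrawal, loss to follow-up or death, whichever is first. Remove the EDV from that list and keep loss to follow-up in it.
- Map Follow-up Visits 1 and 2 that fall in this period to the analysis windows by study day.
- Use the same cut for flare count and flare exposure.
- Keep last dose plus 28 days for the on-treatment flare analysis only.

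If the EDV cut is intended, relabel the strategy in SAP Table 2, declare the departure from Protocol 8.5 in SAP Section 2, and still align count with exposure.

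The cost is minor SAP wording and programming. The assessments are already scheduled in Protocol Table 5.
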